## **10.2 Vital Signs**

Summary statistics for vital signs (systolic blood pressure [SBP] and diastolic blood pressure [DBP] and pulse rate) will be calculated for each time point and for the change from baseline to each time point measured after randomization. Clinical significance will be defined as follows.

- SBP value  $\geq$  160 or Increase (INC)  $\geq$  20
- SBP value  $\leq$  90 or Decrease (DEC)  $\geq$  20
- DBP value  $\geq$  105 or INC  $\geq$  15
- DBP value  $\leq$  50 or DEC  $\geq$  15
- Pulse rate value  $\geq$  120 or INC  $\geq$  15
- Pulse rate value  $\leq$  50 or DEC  $\geq$  15

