Exploratory	
 To compare the efficacy of naldemedine 1.25 mg, 2.5 mg, and 5 mg and placebo for the exploratory endpoints Time from the end of surgery to time to discharge readiness Time from the end of surgery to time of actual discharge (departure) from the hospital Proportion of patients with prolonged hospital stay due to gastrointestinal dysfunction Time from initial insertion of the nasogastric tube to removal of the nasogastric tube Proportion of patients with abdominal distention on Day 1 through the day on which GI2 is achieved Proportion of patients with nausea on Day 4 through day of discharge Proportion of patients with vomiting on Day 4 through day of discharge Proportion of patients who achieve GI2 in each treatment group by postoperative day Proportion of patients who receive concomitant medication that may have a laxative effect Effect of prior surgery (yes/no) on the GI2 endpoint
Pharmacokinetics	
 To characterize the pharmacokinetics (PK) profile of naldemedine 1.25 mg, 2.5 mg, and 5 mg and its metabolite (nor-naldemedine) for the PK endpoints Plasma drug concentrations of naldemedine and nor-naldemedine on: 
 Day 2 immediately before the morning dose Day 3 immediately before the morning dose and 1 hour and 2, 4, 8, and 12 hours after the morning dose before administration of the evening dose Day 4 immediately before the morning dose PK parameters of naldemedine and nor-naldemedine (C_{max}, T_{max}, AUC, CL/F, $MR_{M/U}$, C_{max}, and $MR_{M/U}$, AUC)
Safety	
 To compare the safety of naldemedine 1.25 mg, 2.5 mg, and 5 mg and placebo for the safety endpoints Incidence of treatment-emergent adverse events, including those that are serious and those that result in discontinuation of study treatment

	
• Proportion of patients with clinically significant changes in clinical laboratory tests, vital signs, and ECGs• Change from baseline in pain intensity, as assessed on a Numerical Pain Rating Scale (NPRS)• Total dose of intra- and postoperative opioid analgesics in morphine milligram equivalents (MMEs)
--	--

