9.4.6 Safety Analyses

All safety analyses will be performed on the Safety Population.

Adverse events will be classified by system organ class and preferred term using Medical Dictionary for Regulatory Activities (MedDRA). Adverse events reported after the initial dose of study drug will be considered TEAEs and will be analyzed.

The number and the percentage of patients who experienced TEAEs will be summarized by treatment group. Treatment-emergent SAEs, AEs related to study treatment, and TEAEs leading to discontinuation of study drug will also be summarized by treatment group. The number of occurrences of TEAEs, which are counted among patients reporting those TEAEs, will also be presented in the categories above in an overall summary.

For the summary of TEAEs by system organ class and preferred term, the number and percentage of patients who experienced TEAEs will be presented for each treatment group. A summary of TEAEs by severity and by relationship to study treatment will be presented by system organ class, preferred term, and treatment group.

All AEs, including AEs that have occurred before and after the first dose of the study treatment, will be listed.

Summary statistics for laboratory tests and vital signs will be presented for all time points. The change from baseline to each time point in laboratory tests and vital signs will be summarized. In addition, the proportion of patients with clinically significant changes from baseline in laboratory tests, vital signs, and ECG data will be presented. Criteria for clinically significant changes in laboratory tests, vital signs, and ECG data will be defined in the SAP.

Summary statistics for NPRS, COWS, and intraoperative and postoperative MME opioid dose will be presented for all time points. The COWS score in each domain will be summarized categorically. The opioid dose recorded in the eCRF will be converted to the MME opioid dose using conversion factors. The details will be defined in the SAP.

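### SAP 10.2 counts an unchanged or improved abnormal vital sign toward an endpoint the protocol defines as change from baseline, and gives no counting rule

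*SAP*

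**What the plan says.** The protocol lists this safety endpoint (Synopsis and Table 3-1): "Proportion of patients with clinically significant changes in clinical laboratory tests, vital signs, and ECGs". Protocol 9.4.6 describes the analysis as the proportion with such changes relative to baseline and delegates the definition: "Criteria for clinically significant changes in laboratory tests, vital signs, and ECG data will be defined in the SAP". SAP 10.2 is therefore the operative definition. It introduces six rules with the words "Clinical significance will be defined as follows". All six have the same form, of which the high systolic rule is an example: "SBP value $\geq$ 160 or Increase (INC) $\geq$ 20". The low systolic rule uses a level of 90 and a fall of 20. Diastolic pressure has levels of 105 (high) and 50 (low), and pulse has 120 (high) and 50 (low), all four with a change of 15 as the alternative. No units are given. Baseline is the single last value before randomization (SAP 6.5.2), and vital signs are taken once daily (Protocol 8.2.2).

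SAP 10.2 also provides summary statistics and change from baseline at each time point, but it does not say how patients meeting the rules are to be counted. SAP 10.3 does say so for laboratory tests: at each time point, and at any time in the study. Protocol 8.2.2 separately has investigators judge clinically significant vital-sign changes and record them as adverse events.

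**The concern.** The endpoint is a change, but half of each rule ignores change. A patient who enters with a systolic pressure above the cut-off and stays there contributes to the numerator, as does one whose pressure falls but remains above it. Such patients say something about who was enrolled and nothing about what happened after dosing.

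The missing counting rule adds to this. The endpoint is a proportion of patients, so a programmer could reasonably pool all six rules over all readings. That count would pick up much ordinary day-to-day variation. It would also depend on length of stay, because readings are daily: an arm discharged earlier has fewer chances to be flagged. Time to the discharge order is itself a secondary efficacy endpoint.

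**Working it through.** **Step 1. Apply the rules as written (no assumptions).**

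| Systolic pressure | Change | Level part (160 or above) | Change part (rise of 20 or more) | Counted? |
|---|---|---|---|---|
| 165 to 165 | 0 | met | not met | yes |
| 175 to 162 | -13 | met | not met | yes |

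Neither patient worsened, and the fall of 13 does not reach the low rule's 20 either. Both are counted only because the level part has no baseline condition.

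**Step 2. Inputs for a size estimate.** The documents give no flag rate and no vital-sign SD, so there is no figure of the plan's to reproduce. All of the following are assumptions: means 130/76/76 (systolic/diastolic/pulse); within-patient SDs 6/4/4 (low), 10/6/7 (mid), 13/8/10 (high); between-patient SDs 15/9/10 (low, mid) and 18/11/12 (high); the three signs independent; no drug effect.

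**Step 3. How many patients start beyond the systolic level?** P(baseline at or above 160) = 1 - Phi((160 - 130) / sqrt(between² + within²)).

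- Low: 30 / sqrt(225 + 36) = 1.86, about 3%.
- Mid: 30 / sqrt(225 + 100) = 1.66, about 5%.
- High: 30 / sqrt(324 + 169) = 1.35, about 9%.

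In simulation (200,000 patients), the share of high-systolic flags that come from the level alone, with a rise below 20, is about 77% (low), 31% (mid) and 29% (high).

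**Step 4. Change part at one reading.** P(change at least d in one direction) = 1 - Phi(d / (within SD × sqrt 2)). Mid case:

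- Systolic: 20 / 14.14 gives 0.0786.
- Diastolic: 15 / 8.49 gives 0.0385.
- Pulse: 15 / 9.90 gives 0.0649.

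Doubling each for the two directions and pooling: 1 - (1 - 0.157)(1 - 0.077)(1 - 0.130) = 0.32, which agrees with the simulated 32.2%.

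**Step 5. Full level-or-change rules, simulated with no drug effect.**

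| Count | Low | Mid | High |
|---|---|---|---|
| One criterion, one reading | 0.4-4% | 4-11% | 10-20% |
| One criterion, ever in 6 readings | 2-11% | 16-36% | 33-52% |
| Any criterion, one reading | 8% | 37% | 65% |
| Any criterion, ever in 3 readings | 18% | 69% | 92% |
| Any criterion, ever in 6 readings | 26% | 86% | 99% |

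A second set of assumed means (128/76/78; between-patient SDs 15/9/10) over 3 to 7 readings gives 16% to 27% with within-patient SDs 6/4/4. With SDs from 8/6/7 up to 13/9/11 it gives 59% to about 99%. Hence the overall range of about 16% to 99%.

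**Step 6. What drives the pooled rate?** In the mid case with 6 readings, the change part alone flags 82%, against 86% for the full rule. The volume comes mainly from the size of the change cut-offs, six criteria and repeated readings. The word 'or' adds little to it.

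**Step 7. Does the rule still separate arms?** Assume a 15-unit systolic fall in one arm, within-patient SDs 10/6/7, the second set of means, and 5 readings. The low-systolic criterion rises from about 27% to 76% of patients ever flagged. The pooled any-criterion count rises only from 81% to 91%.

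**The case against.** The strongest reply is that the protocol leaves the criteria to the SAP, that level-or-change screens are a legitimate choice, and that nothing rests on this flag alone. Change from baseline is summarised at every time point, and investigator-judged changes enter the adverse event tables. This largely stands, and it is why the point is minor. It does not answer Step 1: delegating the criteria does not turn an unchanged value into a change.

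A reader might infer more: that most patients will be flagged with no drug effect, so that the endpoint cannot show a difference. The documents do not support this. SAP 10.2 specifies no pooled any-criterion, any-day count. With low variability the pooled rate stays well below half, and for a single criterion at a single time point it is at most about 20%. Step 7 shows that an individual criterion still separates arms clearly.

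A reader might also want level and change required together. That would remove the unchanged baselines, but under the Step 7 variability with no drug effect about 88% of systolic falls of 30 or more at a reading would go uncounted, because the pressure stays above 90. A fall from 150 to 95 would not count. For an endpoint named as change, that is a poor trade. Nor is a change of 15 or 20 within the normal range a fault in itself, since a change endpoint is meant to register it.

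**Conclusion.** The mismatch between endpoint and definition is exact from the text: the level part of each rule can count patients with no change, or an improvement, as having a clinically significant change from baseline. Under the assumptions above, about 3% to 9% of patients would start at or beyond the high systolic level.

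The counting rule is also missing. The pooled range of about 16% to 99% shows only what could happen if an unspecified count were adopted, and it depends almost entirely on the assumed within-patient SD. High background flagging common to all arms dilutes a randomized comparison without biasing it. An ever-flagged count can, however, differ between arms through length of stay alone (mid case: 69% with 3 readings, 86% with 6).

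The severity is minor. This is a descriptive safety summary, and no type I error or power figure is affected.

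**What to change.** Amend SAP 10.2 before database lock:

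- For each of the six criteria, report the change part and the level part as separate rows.
- Count the level part as a change only when the baseline value was not already beyond that same level.
- State that counts are given at each time point and at least once, as SAP 10.3 does for laboratory tests, with the number of patients measured at each time point so that differing stays are visible.
- Add units, and label this flag so that it is not confused with the investigator-judged changes recorded as adverse events.

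Keep the cut-offs as they are, and do not make level-and-change the headline rule.

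The cost is up to twelve table rows (six criteria, two parts each) and a somewhat lower count. If the parts were still pooled, the result would lie between the change-only and the full-rule figures: 82% to 86% in the mid case with 6 readings, 16% to 26% in the low case. New level crossings alone, on any criterion in 6 readings, would be about 9%, 22% and 45% in the low, mid and high cases.

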## **10.3 Laboratory Evaluations**

Summary statistics for laboratory test data will be calculated for each time point and for the change from baseline to each time point measured after randomization. Categorical parameters at each scheduled time point measured at baseline and after randomization will be summarized by using the frequency count and the percentage of patients in each category. Shift tables from baseline to the observed value in each time point will be presented for categorical parameters.

The number and proportion of patients who meet the prespecified criteria shown in Table 5 will be summarized by treatment group for each time point. Patients with laboratory abnormalities at least once throughout the study (including measurements collected outside of the analysis visit window) will be summarized in the same manner.

**Table 5 Criteria for Laboratory Tests**

Laboratory Test (Unit)	Criteria
ALT (U/L)	Value $> 3 \times$ ULN
	Value $> 8 \times$ ULN
AST (U/L)	Value $> 3 \times$ ULN
	Value $> 8 \times$ ULN
AST (U/L) or ALT (U/L)	Value $> 3 \times$ ULN
	Value $> 5 \times$ ULN
	Value $> 8 \times$ ULN
AST (U/L) or ALT (U/L) + total bilirubin (mg/dL) or PT-INR	Meet all of the following criteria: 

• AST <math>\geq 3 \times</math> ULN or ALT <math>\geq 3 \times</math> ULN

• Total bilirubin value <math>\geq 2 \times</math> ULN or PT-INR <math>> 1.5</math>

	Meet all of the following criteria: 

• AST <math>\geq 3 \times</math> ULN or ALT <math>\geq 3 \times</math> ULN

• accompanied by fatigue, nausea, vomiting, right upper quadrant pain or tenderness, fever, rash, and/or eosinophilia (<math>> 5\%</math>)

Total bilirubin	Value $> 2 \times$ ULN
PT-INR	Value $> 1.5$

ALT = alanine aminotransferase; AST = aspartate aminotransferase; INR = international normalized ratio; PT = prothrombin time; ULN = upper limit of normal

#### **10.4 Electrocardiograms**

Electrocardiogram findings (normal, abnormal – not clinically significant, abnormal – clinically significant) will be summarized for each time point measured after randomization by treatment group.

#### **10.5 Physical Examinations**

Summary of the overall assessment by time point will be presented as categories (normal, abnormal – clinically significant, abnormal - not clinically significant, not done). The same summary by body system (autoimmune, cardiovascular, dermatological, ears/nose/throat, endocrine/metabolic, gastrointestinal, genito-urinary, hematologic/lymphatic, hepatic, immunological, musculoskeletal, neurological, ophthalmological, psychological, respiratory) will be presented.

#### **10.6 Pain Intensity as Assessed on Numerical Pain Rating Scale**

Values will be summarized using statistics for continuous variables for all available days. In addition, from Day 2 onwards the change from baseline will be summarized using statistics for continuous variables.

## 10.7 Clinical Opiate Withdrawal Scale

Total scores across all domains will be summarized using statistics for continuous variables on each day. The proportion of patients in each score category by domain will be calculated.

## 10.8 Opioid analgesics

Morphine milligram equivalent (MME) (mg) will be calculated as (dose of opioid analgesics) x (conversion factor). The conversion factor by opioid type is shown in Table 6 below; the table will be updated prior to database lock if additional opioid types need to be added.

MMEs will be summarized as continuous variables on each day.

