Pharmacokinetics	
To characterize the pharmacokinetics (PK) profile of naldemedine 1.25 mg, 2.5 mg, and 5 mg and its metabolite (nor-naldemedine) for the PK endpointsPlasma drug concentrations of naldemedine and nor-naldemedine on:
Day 2 immediately before the morning doseDay 3 immediately before the morning dose and 1 hour and 2, 4, 8, and 12 hours after the morning dose before administration of the evening doseDay 4 immediately before the morning dosePK parameters of naldemedine and nor-naldemedine (C_{max}, T_{max}, AUC, CL/F, $MR_{M/U}$, C_{max}, and $MR_{M/U}$, AUC)
Safety	
To compare the safety of naldemedine 1.25 mg, 2.5 mg, and 5 mg and placebo for the safety endpointsIncidence of treatment-emergent adverse events, including those that are serious and those that result in discontinuation of study treatmentProportion of patients with clinically significant changes in clinical laboratory tests, vital signs, and ECGsChange from baseline in pain intensity, as assessed on a Numerical Pain Rating Scale (NPRS)Total dose of intra- and postoperative opioid analgesics in morphine milligram equivalents (MMEs)

AUC = area under the plasma concentration-time curve; CL/F = apparent total clearance estimated according to: $CL/F = Dose/AUC_{0-\infty}$ on Day 3 (for naldemedine only); C_{max} = maximum observed plasma concentration on Day 3; ECGs = electrocardiograms; $MR_{M/U, AUC}$ = metabolic ratio of $AUC_{0-\infty}$ of nor-naldemedine to $AUC_{0-\infty}$ of naldemedine, corrected for molecular weight, defined as $(\text{nor-naldemedine } AUC_{0-\infty})/(\text{naldemedine } AUC_{0-\infty}) \times (\text{naldemedine molecular weight } [570.64])/(\text{nor-naldemedine molecular weight } [516.55])$ (for nor-naldemedine only); $MR_{M/U, C_{max}}$ = metabolic ratio of C_{max} of nor-naldemedine to C_{max} of naldemedine, corrected for molecular weight, defined as $(\text{nor-naldemedine } C_{max})/(\text{naldemedine } C_{max}) \times (\text{naldemedine molecular weight } [570.64])/(\text{nor-naldemedine molecular weight } [516.55])$ (for nor-naldemedine only); T_{max} = time to maximum plasma concentration on Day 3

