5.1 Inclusion Criteria

Patients are eligible to be included in the study only if all of the following criteria apply:

Age

1. Patient must be 18 to 80 years of age, inclusive, at the time of signing the informed consent form (ICF).

Type of Patient and Disease Characteristics

2. Scheduled to undergo 1 of the following procedures via open (nonlaparoscopic) surgery under general anesthesia:
 - partial small or large bowel resection with primary anastomosis
 - radical cystectomy requiring bowel transection with primary anastomosis
3. Planned to be managed postoperatively with an enhanced recovery protocol, which, at a minimum, includes all of the following elements:
 - early removal of the nasogastric tube, which is defined as removal of the nasogastric tube at the end of surgery
 - early ambulation, which is defined as ambulation on Day 1
 - early diet advancement on Day 1
4. Planned to receive primary postoperative pain management with opioid analgesia administered by any route.
5. American Society of Anesthesiologists (ASA) Physical Status Score of I, II, or III (a normal healthy patient, a patient with mild systemic disease, or a patient with systemic disease, respectively).

Sex

6. Male or female

Male patients:

- There are no specific requirements for contraceptive measures for male patients.

Female patients:

- A female patient is eligible to participate if she is not pregnant (negative urine pregnancy test at Screening for a woman of childbearing potential [WOCBP]; see also [Appendix 4](#)), not breastfeeding, and at least 1 of the following conditions applies:
 - i. Postmenopausal (defined as at least 12 months of spontaneous amenorrhea in a woman > 45 years)

- ii. Surgically sterile by hysterectomy, bilateral oophorectomy, and/or bilateral salpingectomy or tubal ligation
- iii. Agree to use an acceptable effective form of birth control (with failure rates > 1% per year) from the start of Screening through 14 days after the last dose of study treatment, such as:
 - (a) Progestogen-only oral hormonal contraception (where inhibition of ovulation is not the primary mode of action)
 - (b) Male or female condom with or without spermicide
 - (c) Cap, diaphragm, or sponge with spermicide

Informed Consent

- 7. Capable of giving signed informed consent as described in [Appendix 1](#), which includes compliance with the requirements and restrictions listed in the ICF.

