6.5 Medical History and Prior and Concomitant Therapy

Any prior history of postoperative ileus and postoperative gastrointestinal dysfunction must be recorded on the eCRF as part of the patient's medical history.

Any medication or vaccine (including over-the-counter or prescription medicines, vitamins, and herbal supplements) that the patient is receiving at the time of enrollment or receives during the study must be recorded in the eCRF along with the following information:

- Reason for use
- Dates of administration including start and end dates
- Dosage information including dose, route of administration, and frequency

The preoperative bowel preparation, if any, must be recorded in the eCRF. Additionally, the total volume of intravenous fluids administered during the surgery must be recorded in the eCRF.

The CRO's medical monitor should be contacted if there are any questions regarding permissible prior or concomitant therapy.

In addition to the prior and concomitant therapy exclusions in [Section 5.2](#), the following medications are prohibited for 14 days before the first dose of study treatment and through the end of study treatment:

- Strong cytochrome P450 3A (CYP3A) inducers (eg, carbamazepine, enzalutamide, mitotane, phenytoin, rifampin, St. John's Wort) (see [Appendix 6](#))
- Strong CYP3A and P-glycoprotein (P-gp) inhibitors (eg, clarithromycin, diltiazem, grapefruit juice, indinavir, ketoconazole, ritonavir) (see [Appendix 7](#))
- Other opioid antagonists
- Prophylactic use of laxatives (eg, magnesium citrate, magnesium hydroxide, magnesium sulfate, castor oil, sodium phosphate, sodium biphosphate, polyethylene glycol enemas, and stimulant laxatives, including bisacodyl); however, if needed, laxatives may be used for rescue therapy

Re-insertion of the nasogastric tube is permitted if needed (see [Section 8.1.2.2](#)).

The following elements of the enhanced recovery protocol at the study site must be recorded as yes or no in the eCRF at Baseline (planned) and at the day of discharge or early termination (actual):

- Three elements required by the protocol:
 - Early removal of the nasogastric tube, defined as removal of the nasogastric tube at the end of surgery
 - Early ambulation, defined as ambulation on Day 1
 - Early diet advancement on Day 1
- Four other elements that may be used at the study site:
 - Antibiotic prophylaxis
 - Preoperative carbohydrate drink
 - Epidural anesthesia in addition to general anesthesia

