**Table 6 Conversion Factor**

Opioid Type (Route)	Unit	Conversion Factor
LEVOMETHADONE	mg	8
LEVORPHANOL	mg	7.5
HYDROMORPHONE	mg	4
METHADONE	mg	4
OXYMORPHONE	mg	3
FENTANYL (Topical or Transdermal)	ug/hour	2.4
OXYCODONE	mg	1.5
HYDROCODONE	mg	1
MORPHINE	mg	1
CODEINE	mg	0.15
DIHYDROCODEINE	mg	0.15
FENTANYL (Intravenous, Sublingual or Transmucosal)	ug	0.1
MEPERIDINE	mg	0.1
BUTORPHANOL	mg	0
PENTAZOCINE	mg	0
TAPENTADOL	mg	0
TRAMADOL	mg	0
BUPRENORPHINE	mg	0
SUFENTANIL	mg	0

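### MME is computed with one factor per opioid whatever the route, so the between-arm opioid safety endpoint mixes opioid need with route of administration, in a direction the documents do not fix

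*SAP*

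**What the plan says.** SAP 10.8 gives the formula: "Morphine milligram equivalent (MME) (mg) will be calculated as (dose of opioid analgesics) x (conversion factor"). It has no term for route. The source of the factor is described next: "The conversion factor by opioid type is shown in Table 6 below; the table will be updated prior to database lock if additional opioid types" have to be added.

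The first column of Table 6 is headed "Opioid Type (Route"), but only two of its 19 rows name a route. These are "FENTANYL (Topical or Transdermal") at 2.4 per µg/hour and "FENTANYL (Intravenous, Sublingual or Transmucosal") at 0.1 per µg. Morphine (1), hydromorphone (4), methadone (4), oxymorphone (3), oxycodone (1.5) and meperidine (0.1) each have a single factor with no route. Six opioids have factor 0: butorphanol, pentazocine, tapentadol, tramadol, buprenorphine and sufentanil. The table does not say whether its reference is oral or parenteral morphine.

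Protocol Section 3 lists this safety endpoint: "Total dose of intra- and postoperative opioid analgesics in morphine milligram equivalents (MMEs"). It sits under the objective of comparing safety between the three doses and placebo. Protocol 9.4.6 leaves the conversion details to the SAP. Inclusion criterion 4 (Protocol 5.1) reads: "Planned to receive primary postoperative pain management with opioid analgesia administered by any route". For each medication, Protocol 6.5 requires the eCRF to hold "Dosage information including dose, route of administration, and frequency". SAP 10.8 plans only a descriptive summary of MME by day, with no test.

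**The concern.** An equivalence measure is useful when the same number means the same opioid effect. Under SAP 10.8, a milligram of morphine adds 1 MME whether it is given intravenously, by mouth or by the epidural route. If these routes are not equipotent, two patients with the same analgesic need get different MME totals because their routes differ.

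Mixed routes are to be expected here. Any route is allowed, the endpoint adds intra-operative to postoperative opioid, and diet advancement is planned for Day 1, so oral dosing within the measured days is plausible. The drug is a mu-opioid antagonist, so opioid consumption by arm helps to interpret the pain scores. If the route mix differs between arms, an MME difference could appear with no difference in need, or a real difference could be masked.

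**Working it through.** Neither document states an expected MME or a route ratio, so there is no planned figure to reproduce.

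**1. Is fentanyl a route adjustment?** Table 6 gives 0.1 per µg (intravenous, sublingual, transmucosal) and 2.4 per µg/hour (topical, transdermal). Over a day, 0.1 × 24 h = 2.4. Each microgram delivered has the same weight in both rows, so they differ in unit and not in potency by route. Epidural fentanyl fits neither row.

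**2. Size under equal need.** Let M be the daily intravenous morphine dose in mg, s the day of switch to oral, T the days counted, and r the oral mg equal in effect to 1 mg intravenous. With the Table 6 morphine factor of 1 for both routes,

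MME = M·s + r·M·(T − s).

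None of M, s, T or r is in the documents. Assumptions: M = 20 mg/day, T = 5, s = 3 in the slower arm and s = 2 in the faster arm, r = 1 to 3. The one-day lead borrows the 24-hour design difference in GI2 (Protocol 9.2) purely as an illustration.

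| r | switch at day 3 | switch at day 2 | difference |
|---|---|---|---|
| 1 | 60 + 40 = 100 | 40 + 60 = 100 | 0 |
| 1.5 | 60 + 60 = 120 | 40 + 90 = 130 | +10 (8.3%) |
| 2 | 60 + 80 = 140 | 40 + 120 = 160 | +20 (14.3%) |
| 3 | 60 + 120 = 180 | 40 + 180 = 220 | +40 (22.2%) |

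The difference is (r − 1)·M and the relative difference is (r − 1)/(3 + 2r), so the percentages do not depend on M. For an 18-hour lead, multiply by 0.75: 6.2%, 10.7% and 16.7% for r = 1.5, 2 and 3.

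**3. Zero-factor opioids.** Let q be the share of oral use given as a zero-factor opioid. Moving one day from intravenous to oral then changes MME by M·[(1 − q)·r − 1], which is negative once q > 1 − 1/r. The thresholds are 33% at r = 1.5, 50% at r = 2 and 67% at r = 3. At q = 1 and M = 20, the earlier-switching arm shows 20 MME less at every r.

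**4. After correction.** Give intravenous morphine a factor r times the oral one. The total becomes r·M·s + r·M·(T − s) = r·M·T, which does not depend on s, so the arm difference is 0 for every M, r and lead. This holds for q = 0. With zero factors kept, the moved day changes MME from r·M to (1 − q)·r·M, a change of −q·r·M. At q = 0.5, r = 2 and M = 20 that is −20. Route-specific factors alone are therefore not enough, and the zero factors need attention too.

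**The case against.** A reader might infer that the arm recovering gut function sooner will appear to need more opioid. The documents do not support this. No passage says that GI recovery determines the change to oral opioid. GI2 is the later of tolerating solid food and first bowel movement, and nothing ties oral analgesia to a bowel movement. Every arm is planned for diet advancement on Day 1, and study drug is itself an oral tablet from Day 0. A difference in GI2 need not produce an equal difference in the time of switch. The zero factors can also reverse the sign.

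The size is illustrative as well. A full day's lead equals the whole design difference, which is assumed only for 5 mg against placebo. If the trend is linear on the equally spaced scale of the SAP 9.1.1 contrast, the lower doses would lead by 8 and 16 hours. At r = 2 the inflation then falls to 14.3% × 1/3 = 4.8% and 14.3% × 2/3 = 9.5%. Equal intra-operative opioid in both arms would dilute the percentages further, though not the absolute difference.

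Nor is MME the sole or main check on analgesia. Pain intensity is a separate named safety endpoint, COWS is summarized daily, and no test or decision rule uses MME. SAP 10.8 does not forbid adding routes; it simply makes no commitment to do so. Epidural anesthesia is a recorded recovery element, but the documents do not say that it contains an opioid.

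All of this stands, and it removes any claim about direction or expected arm difference. The stated rule still counts equal milligrams by different routes as equal MME, in an endpoint meant for comparison across arms.

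**Conclusion.** The point holds without a fixed direction. As written, Table 6 makes no adjustment for route potency, states no reference route and has no row for epidural fentanyl, so total MME is confounded with route mix.

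The 8% to 22% rests on two assumptions from outside the documents: an oral dose 1.5 to 3 times the intravenous dose for equal effect, and a switch about a day earlier in one arm. With r = 1 there is no distortion. With an oral zero-factor share above 1 − 1/r the sign is negative. The figures compare hypothetical patients with identical need and do not forecast the trial result. The consequence is confined to a descriptive safety summary; the GI2 analysis and the sample size are untouched. It should be corrected because the endpoint is named and comparative, and the data needed are already collected.

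**What to change.** Before unblinding, revise SAP 10.8 and Table 6 to:

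- state the reference (oral or parenteral morphine);
- give analysis conversion factors by opioid and route (parenteral, oral, neuraxial) from one named source, including epidural fentanyl;
- justify each zero factor or replace it;
- extend the planned update before database lock to cover routes as well as opioid types;
- tabulate MME by route beside the total for each arm, so that a shift in route mix is visible.

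The cost is one SAP table revision and one added table. Route is already an eCRF item under Protocol 6.5, so no new data are needed. The change concerns analysis conversion only and implies nothing about how opioids are dosed or chosen.
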